### **3.3 Early Withdrawal of Subjects**

#### **3.3.1 Criteria for removal from study**

1. Withdrawal of parental permission
2. Child develops significant laryngospasm that needs intervention with succinylcholine

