#### **3.3.2 Follow-up for withdrawn subjects**

Not applicable

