## 7.2 Study Procedures

### 7.2.1 Day of Surgery

After obtaining informed consent, the infant will be randomized to the vein visualization or standard group based on a computer generated number.

Standard anesthesia induction procedures will be used. This includes application of standard ASA monitoring at induction and standard inhalation induction with sevoflurane.

Once the subject is deemed ready for intravenous access attempt, a tourniquet will be applied on the corresponding limb where IV access is contemplated.

For those randomized to the control group (standard technique group), the standard technique for establishing IV access will be used. The standard technique involves directly identifying the vein after application of a tourniquet, cleaning with alcohol and then siting the intravenous catheter.

For those randomized to the vein visualization group, the AccuVein device will be used as an aid to identify the vein after application of a tourniquet. The technique of actual insertion of the intravenous catheter will be the same as the standard technique. The device will be used to better visualize and identify the vein.

If, after 3 needle sticks, IV access has not been established using the technique for the group to which the subject was assigned (standard or vein finder), the care provider will use the other technique (standard or vein finder) to attempt to insert the IV line.

In order to avoid operator variation, the intravenous catheter will be inserted by an experienced pediatric anesthesiologist who is a member of the research team. Currently all the pediatric anesthesia faculty members are familiar with, and have used, the vein finder in case of difficult intravenous access. If a complication develops while attempting to start an IV using the vein finder or standard technique, and a rapid IV access is needed, it will be at the attending anesthesiologist's discretion to perform the IV rapidly with either technique, since our faculty anesthesiologists are proficient with both techniques. Multiple anesthesiologists may attempt the IV simultaneously. This is how we would normally manage this situation and is the standard of care. If this happens we will withdraw the child from the study.

Data to be collected:

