The time to successful IV insertion will be from the first time that the canula touches the skin to until successful IV access; up to 3 attempts. After the 3rd attempt, if still unsuccessful, the alternative technique will be used as rescue. Again, time to successful insertion will be noted. Success at IV will be determined by flushability with 5 ml of sterile normal saline. The site(s) of access will also be recorded.

Medical Record Information: This information will include, but is not limited to: Age, gender, physical status, weight, height, skin color, surgical procedure, presenting underlying conditions and co-morbidities.

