## 7.3 Duration of Participation

Patient participation will end at the end of surgery.

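### Children withdrawn after randomization because a complication during the IV attempt calls for rapid access have no stated place in the primary analysis, and leaving them out can bias the comparison of success rates

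*Combined protocol and SAP*

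**What the plan says.** Randomization takes place after consent and before induction (section 7.2.1). The primary endpoint is IV success within three attempts (1.2). Section 7.2.1 then separates two situations.

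- **Ordinary failure.** "After the 3rd attempt, if still unsuccessful, the alternative technique will be used as rescue", and the time to success is still noted. Nothing in this rule removes the child from the study.
- **Complication.** "If a complication develops while attempting to start an IV using the vein finder or standard technique, and a rapid IV access is needed", the attending anesthesiologist may "perform the IV rapidly with either technique". In addition, "Multiple anesthesiologists may attempt the IV simultaneously". The consequence is: "If this happens we will withdraw the child from the study".

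Section 3.3.1 lists two reasons for removal: withdrawal of parental permission, and "Child develops significant laryngospasm that needs intervention with succinylcholine". The rapid-access rule of 7.2.1 is not on that list, and the laryngospasm criterion has no time limit. Section 3.3.2, on follow-up of withdrawn subjects, is marked not applicable. Section 7.3 says: "Patient participation will end at the end of surgery".

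Section 8.1 raises the sample size by 15% to 160 to cover withdrawals and incomplete data. Section 8.3 names the software, a 0.05 threshold, a chi-square test for attempts and ANOVA for times. It gives no analysis population and no rule for a child whose attempt is interrupted.

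**The concern.** The withdrawal comes after allocation and is triggered during the procedure that the trial compares. A child whose IV takes longer or needs more sticks is plausibly exposed for longer to a complication that makes rapid access necessary. If one technique leads to longer attempts, withdrawals can then differ between arms and be concentrated among children who were not succeeding. The people judging that rapid access is needed also know which technique is in use.

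If these children are dropped, the groups compared are no longer quite the randomized ones. If they are kept, the protocol does not say how to score them. With either technique allowed and several operators at work, two analysts could code the same record differently. Urgent access at induction is also the situation that section 2.1 gives as the reason for studying IV placement in infants.

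**Working it through.** **1. What the sample size implies about withdrawn children.** Section 8.2 gives 139 from a 90% success rate and 95% confidence. The figure is reproduced by a single-proportion precision formula with an assumed half-width of 5 points, which the protocol does not state: n = 1.96² × 0.90 × 0.10 / 0.05² = 138.3, rounded up to 139. Then 139 × 1.15 = 159.85, rounded up to 160, as in 8.1. The margin is 21 children, or 21/160 = 13.1% of those enrolled. So the plan expects that some enrolled children will not contribute. A margin protects numbers, not comparability.

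**2. Direction.** Suppose an arm has s successes among n children, and w children are left out, of whom a fraction f would have succeeded. The rate changes from s/n to (s − fw)/(n − w). It rises if f is below s/n and falls if f is above it. The protocol gives neither w nor f for either arm, so the difference can move either way.

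**3. Size per child.** Leaving out one failure raises the arm's rate by s/(n − 1) − s/n = s/[n(n − 1)]. With n = 80 this is 72/6320 = 1.1 points at 90%, 64/6320 = 1.0 at 80%, 60/6320 = 0.9 at 75% and 56/6320 = 0.9 at 70%.

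**4. Effect on the test (illustration only).** Assumptions: 80 per arm (the allocation ratio is not stated), 90% with the device (8.2), and control rates of 70% to 85% (none is stated). Withdrawn children are failures unless noted. The test is the Pearson chi-square, N(ad − bc)² divided by the product of the four margins. Example: for 72/80 v 60/80, 160 × 960² / (80 × 80 × 132 × 28) = 6.23, p = 0.013. With four standard-arm failures left out (60/76), 156 × 672² / (80 × 76 × 132 × 24) = 3.66, p = 0.056. Continuity-corrected p-values are in brackets.

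| Left out | Device v standard | Difference (points) | p |
|---|---|---|---|
| None | 72/80 v 56/80 | 20.0 | 0.002 [0.003] |
| 8 standard | 72/80 v 56/72 | 12.2 | 0.039 [0.066] |
| None | 72/80 v 60/80 | 15.0 | 0.013 [0.022] |
| 2 standard | 72/80 v 60/78 | 13.1 | 0.027 [0.045] |
| 4 standard | 72/80 v 60/76 | 11.1 | 0.056 [0.091] |
| 4 standard, 2 of them would-be successes | 72/80 v 58/76 | 13.7 | 0.022 [0.038] |
| 1 per arm | 72/79 v 60/79 | 15.2 | 0.010 [0.018] |
| None | 72/80 v 64/80 | 10.0 | 0.077 [0.121] |
| 1 device | 72/79 v 64/80 | 11.1 | 0.046 [0.077] |
| 2 device | 72/78 v 64/80 | 12.3 | 0.026 [0.045] |
| 1 per arm | 72/79 v 64/79 | 10.1 | 0.066 [0.108] |
| 4 per arm | 72/76 v 64/76 | 10.5 | 0.034 [0.064] |
| None | 72/80 v 68/80 | 5.0 | 0.34 [0.47] |
| 2 device | 72/78 v 68/80 | 7.3 | 0.15 [0.23] |

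Uneven losses can push the result across 0.05 in either direction, but only from a starting point close to it. Balanced losses barely move the difference, although four per arm is enough to move an uncorrected p from 0.077 to 0.034.

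**The case against.** Exclusion from the analysis is inferred. To withdraw a child from the study need not mean deleting what was already recorded, and the 15% margin also covers incomplete data. The not-applicable entry for follow-up is weak evidence, since participation ends with surgery for every child and there is no later follow-up to describe. All of this stands. A reader might infer that the protocol says withdrawn children are left out; it does not. What remains is that withdrawal is the stated rule and no analysis rule counteracts it, so leaving them out is the most natural way to follow the plan.

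The events may be rare. Emergency procedures and ASA 4 patients are excluded, operators are experienced, and two conditions must both hold: a complication during the attempt and a need for rapid access. That longer attempts raise the risk is plausible, but the protocol offers no data on it. This stands too, and it limits the size of the concern.

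The illustrations mostly withdraw children from one arm and treat nearly all of them as failures. Eight withdrawals from the standard arm alone, 10% of it, still leave an uncorrected p of 0.039 when the control rate is 70%. The crossing from a single event at a control rate of 80% disappears with continuity correction. The p-values are therefore a sensitivity range, not a forecast.

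The laryngospasm strand is weaker. A reader might infer that a laryngospasm later in surgery erases an IV outcome already observed. That depends on a literal reading of a criterion with no time limit; nowhere does the protocol say recorded data would be discarded.

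**Conclusion.** The concern holds in this form: a stated rule withdraws children after randomization on a trigger that arises during measurement of the primary endpoint, and nothing says how they count. If they are left out, as the plan implies, the comparison of success rates can be biased. The laryngospasm criterion has the same gap, and the removal rules in 3.3.1 and 7.2.1 do not match.

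Size and direction are unknown. The illustrations rest on 80 per arm, assumed control rates and assumed withdrawals. In them a few uneven events alter the conclusion only near p = 0.05. The documents do not support a claim that the trial is biased towards the device, or that the result will be wrong. Nor do they support a claim that ordinary failures are lost: after three sticks those children cross over and their time is still recorded. The point should be fixed because the remedy is cheap and is best settled before any results are seen.

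**What to change.** Clinical care stays exactly as written; only data and analysis rules change.

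1. **Sections 7.2.1 and 3.3.1.** For these events, replace withdrawal from the study with: stop the study procedure, record the event and its timing, and keep the child's data unless parental permission is withdrawn. Reconcile the two lists.
2. **Section 8.3, analysis set.** Analyse all randomized children with permission in the assigned group, using one boundary. Children with no needle stick before the event are reported by arm and left out of the primary analysis; children with at least one stick are included. This fits the time endpoint, which already starts at first skin contact.
3. **Section 8.3, scoring.** For included children, success means access with the assigned technique, within three sticks and before the event. An interrupted attempt counts as not successful. An outcome observed before the event is kept.
4. **Reporting.** Give the events by arm. Repeat the primary analysis excluding the interrupted children, and again with all randomized children who have permission, counting those with no stick as not successful. The second analysis is needed because the boundary in item 2 still omits some randomized children.

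The cost is wording in three sections and two items on the data form: the timing of the event and the number of sticks before it. Sticks made after the event need not be counted for the primary endpoint, which avoids tallying several operators during an emergency. No extra patients are needed. The downside is that some complications unrelated to technique count as not successful, so success rates may look slightly lower. This scoring is one defensible choice among several, and the sensitivity analyses show how much it matters.

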## 7.3 Duration of Participation

Patient participation will end at the end of surgery.

## 8.0 Subject Numbers and Statistical Plan

### 8.1 Number of Subjects

A sample size of 160 patients to include a 15% margin above the number indicated by the sample size determination, to allow for subject withdrawal or situations of incomplete subject data.

### 8.2 Sample size determination

Assuming 90% success rate with the vein visualization device and 95% confidence level, a sample size of 139 patients would be needed to be enrolled in the study.

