## 1.0 Objectives

### 1.1 Study Objectives

Assess the efficacy of the vein visualization device AccuVein (AccuVein, Inc., Huntington, NY) in comparison to a standard technique for establishing intravenous (IV) access in the infant population (<2 years old)

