### 1.2 Primary Study Endpoints

Success Rate of IV Insertion within three allowed attempts

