### 2.2 Previous Data

The success rate at first attempt IV induction in children varies from 32 – 92% depending on provider experience. Various techniques have been tried in the past that include application of warming devices and use of ultrasound. Recent literature suggests use of infrared illumination to aid vein visualization, with a device such as the AccuVein (AccuVein, Inc., Huntington, NY), has been successfully used.

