## **7.0 Study Design and Procedures**

### **7.1 Study Design**

This will be a randomized controlled study.

The objective of the study is to assess the efficacy of the vein visualization device in comparison to a standard technique in the infant population (<2years). Subjects will be randomized to the vein visualization or standard group using a computer generated randomization program.

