### 8.3 Statistical methods

Sigmastat software will be used for statistical analysis. A p-value<0.05 will be considered significant. For statistical analysis, a chi square test will be used for comparing data on attempts and ANOVA for comparing data on times.

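### The inputs reported in Section 8.2 (a 90% device-arm success rate and a 95% confidence level) are not sufficient to size the two-group comparison for which 139 patients are said to be needed

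*Combined protocol and SAP*

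**What the plan says.** The objective (Section 1.1) is to assess the device "in comparison to a standard technique for establishing intravenous (IV) access in the infant population". The primary endpoint (Section 1.2) is "Success Rate of IV Insertion within three allowed attempts". The design has two randomized groups (Section 7.1): "Subjects will be randomized to the vein visualization or standard group using a computer generated randomization program". On testing, Section 8.3 says: "A p-value<0.05 will be considered significant. For statistical analysis, a chi square test will be used for comparing data on attempts".

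The whole sample-size justification is one sentence in Section 8.2: "Assuming 90% success rate with the vein visualization device and 95% confidence level, a sample size of 139 patients would be needed". Section 8.1 then sets "A sample size of 160 patients to include a 15% margin above the number indicated by the sample size determination".

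The only background success rate is in Section 2.2: "The success rate at first attempt IV induction in children varies from 32 – 92% depending on provider experience". Section 8.2 does not use it.

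**The concern.** Sizing a test of two proportions needs an expected rate in each arm (or one rate and a difference), a significance level, a power and an allocation ratio. Section 8.2 reports one rate, for the device arm only, and a confidence level. The rest appears nowhere in the protocol. Nor does Section 8.2 say that its 90% refers to success within three attempts.

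What is at stake is the pre-trial justification for enrolling 160 infants. A reader cannot tell what difference the trial was planned to detect, or with what probability, yet the text presents 139 as the number required.

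**Working it through.** **Inputs from the protocol.** Device success 90% and 95% confidence (8.2); 139 patients (8.2); 15% margin and 160 patients (8.1); significance at p<0.05 and a chi-square for data on attempts (8.3).

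**Assumptions, not in the protocol.** 1:1 allocation, so 139/2 = 69.5 per arm; two-sided testing; the chi-square of 8.3 applied to three-attempt success; the 90% taken as the three-attempt rate; 139 taken as the number analysed; every control rate below.

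**1. Reproducing 139.** The formula for estimating one proportion to within ±d is n = 1.96² × p(1−p) / d². With p = 0.90 and an assumed d = 0.05:

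1.96² × 0.90 × 0.10 / 0.05² = 138.3, rounded up to 139.

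Margins of 4 or 6 points would give 217 or 97. The match is exact, but the protocol states neither the margin nor the formula.

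**2. Reproducing 160.** 139 × 1.15 = 159.85, rounded up to 160. This agrees with Section 8.1.

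**3. If step 1 was the method.** Then 139 is the number for one group. Split over two arms, the 95% half-widths are:

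- device arm alone: 1.96 × √(0.09/69.5) = 0.071, about ±7 points;
- difference, both rates 90%: 1.96 × √(0.18/69.5) = 0.100, about ±10 points;
- difference, 90% against 80%: 1.96 × √(0.25/69.5) = 0.118, about ±12 points.

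**4. Power of the two-group test.** With n per arm, device rate a, control rate b and mean rate m = (a+b)/2:

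power = Φ{ [ |a−b| − 1.96 × √(2m(1−m)/n) ] / √([a(1−a)+b(1−b)]/n) }

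Example, a = 0.90, b = 0.80, n = 69.5: the standard error under no difference is √(0.255/69.5) = 0.0606, and under the alternative √(0.25/69.5) = 0.0600. Then (0.10 − 1.96 × 0.0606)/0.0600 = −0.31, and Φ(−0.31) is about 0.38.

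The exact columns sum the binomial probabilities of all outcomes with 70 and 69 patients for which the chi-square exceeds 3.84.

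| Assumed control rate | 139, formula, uncorrected | 70/69, exact, uncorrected | 70/69, exact, continuity-corrected | 160, formula, uncorrected |
|---|---|---|---|---|
| 60% | 99% | 99% | 98% | 99.5% |
| 65% | 95% | 96% | 93% | 97% |
| 70% | 85% | 86% | 80% | 89% |
| 75% | 65% | 67% | 57% | 71% |
| 80% | 38% | 39% | 29% | 42% |
| 85% | 14% | 14% | 9% | 16% |

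By the uncorrected formula, 139 patients give 80% power when the control rate is about 71% or lower.

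**5. Do the documents narrow the control rate?** Section 2.1 describes infants as a particularly difficult group for IV access, which allows a lower rate. Section 7.2.1 says that "the intravenous catheter will be inserted by an experienced pediatric anesthesiologist who is a member of the research team", which allows a higher one. The 32–92% in Section 2.2 is a first-attempt rate in children across levels of provider experience. Three-attempt success cannot be below first-attempt success in the same patients, but the range does not fix a control rate for infants treated by experienced staff.

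**The case against.** The strongest case on the other side is that 139 may be adequate. At a control rate of 60% or 65% the power is 99% or 95%, and the protocol itself calls infants difficult. An unreported two-group calculation could also have led to a number near 139. And since enrolment stays at 160 under the fix below, this may look like a reporting correction only.

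Much of this stands, and it rules out several stronger readings that a reader might infer:

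- *That the trial is underpowered.* The documents do not show this. Without a control rate, the power could be high or low.
- *That 139 was derived by the one-proportion formula.* The match is exact but needs a margin that is stated nowhere. Section 8.2 shows which inputs were reported, not how the number was obtained.
- *That a non-significant result could not be interpreted.* A confidence interval for the observed difference would show which differences remain compatible with the data, whatever Section 8.2 says.
- *That the step to 160 is wrong.* Section 8.1 describes a margin above the calculated number, and 160 is that. A 15% loss from 160 would leave 136, but this is a minor matter.

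The objection does not supply the missing inputs. Section 8.2 is a complete sentence with no sign of redaction, and no other section fills the gap. Nor can a corrected sample size be given here, because it would rest on a control rate that the documents do not contain.

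**Conclusion.** The point holds in this form: the inputs reported in Section 8.2 are insufficient to size the comparison the trial makes, so the statement that 139 patients are needed is unsupported. This conclusion rests on the text alone and does not depend on how 139 was reached.

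The size is the spread in power that the plan leaves open: from about 99% down to 14% over assumed control rates of 60% to 85% (98% down to 9% with continuity correction). It is conditional on the listed assumptions, including that the 90% is a three-attempt rate. The point should be corrected, because the stated justification for the number enrolled does not address the primary comparison and the correction is cheap.

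**What to change.** Keep enrolment at 160. Replace Section 8.2 with a two-group statement that gives:

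1. the expected success within three attempts in each arm, with its basis (a cited source or the site's own records), saying whether the 90% refers to this endpoint;
2. 1:1 allocation, two-sided alpha of 0.05, and whether the chi-square is continuity-corrected;
3. the resulting power, or the smallest detectable difference, calculated from those inputs.

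The control rate should not be chosen to fit 139, and the claim that 139 is needed should go unless this calculation supports it.

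In Section 8.3, add that the primary result is reported as the difference in three-attempt success with a 95% confidence interval, and that a non-significant result is interpreted from that interval.

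Cost: rewording of 8.2 and one sentence in 8.3, with no added patients and no new data. The downside is that a basis for the control rate has to be found and documented, and that the stated power may be less favourable than the present wording implies.

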### 8.3 Statistical methods

Sigmastat software will be used for statistical analysis. A p-value<0.05 will be considered significant. For statistical analysis, a chi square test will be used for comparing data on attempts and ANOVA for comparing data on times.

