### 1.3 Secondary Study Endpoints

Total number of attempts and time to successful insertion

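### The ANOVA of times has no defined value for a child who fails three attempts, which can change the secondary time result if such failures are common and unequal between arms

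*Combined protocol and SAP*

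**What the plan says.** The primary endpoint (Section 1.2) is "Success Rate of IV Insertion within three allowed attempts". The secondary endpoints (Section 1.3) are "Total number of attempts and time to successful insertion".

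The whole analysis plan for the secondary endpoints is one clause in Section 8.3: "a chi square test will be used for comparing data on attempts and ANOVA for comparing data on times".

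Section 7.2.1 starts the clock at first skin contact and runs it "until successful IV access; up to 3 attempts". It continues: "After the 3rd attempt, if still unsuccessful, the alternative technique will be used as rescue. Again, time to successful insertion will be noted".

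Two rules remove children after randomisation. Section 3.3.1 lists, besides withdrawn permission, "Child develops significant laryngospasm that needs intervention with succinylcholine". Section 7.2.1 covers a complication that calls for rapid access: "If this happens we will withdraw the child from the study". Neither rule removes a child merely because three sticks failed.

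Section 8.2 sizes the trial with "Assuming 90% success rate with the vein visualization device". It does not say whether this means first-attempt or three-attempt success, and it gives no rate for the standard arm.

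**The concern.** A three-stick failure has no time under the plan's own definition. The text does not say whether the rescue time enters the ANOVA, or when its clock starts. The readings are:

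1. **Failures dropped.** This is what an ANOVA run as written tends to do. It compares only the successes, so each arm is cut down by the primary outcome after randomisation.
2. **Valued at the end of attempt 3.** A failure then counts like a success at that moment.
3. **Total time through rescue.** This is a legitimate comparison of starting with the device against starting with standard technique, but it is not stated and it includes time on the other arm's technique.
4. **Clock restarted at rescue.** A three-stick failure can then count as a short time.

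At stake is the secondary time result, one of the two outcomes on which Section 12.2 promises evidence. The primary success rate is not affected.

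**Working it through.** **The plan's own figures.** No figure is given for times. The 139 in Section 8.2 matches a single-proportion precision formula: 1.96² × 0.9 × 0.1 / 0.05² = 138.3, rounded up to 139 (the 5-point half-width is inferred). Section 8.1 follows: 139 × 1.15 = 159.85, so 160. Neither figure bears on the time comparison.

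**Number of children concerned.** Assume that the 90% is three-attempt success and that 139 are split 1:1, about 69 per arm. Device failures: 69 × 0.10 = 6.9. If the standard arm reaches 75% (assumed): 69 × 0.25 = 17.25.

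**Expected times in closed form.** Assume constant per-stick success p, a mean of m = 60 s per stick, and rescue continued to access at the other arm's per-stick success. With three-attempt success S, q = (1 − S)^(1/3), p = 1 − q and K = p + 2pq + 3pq²:

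- dropped = mK/S
- end of attempt 3 = m[K + 3(1 − S)]
- total = end of attempt 3 + (1 − S)R
- restarted = mK + (1 − S)R

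Here R = m / (other arm's p).

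Device, S = 0.90: p = 0.536, K = 1.380. Standard, S = 0.75: p = 0.370, K = 1.277. R is 60/0.370 = 162.1 s for device failures and 60/0.536 = 112.0 s for standard failures.

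| Reading | Standard (s) | Device (s) | Difference (s) |
|---|---|---|---|
| Dropped | 102.1 | 92.0 | 10.2 |
| End of attempt 3 | 121.6 | 100.8 | 20.8 |
| Total | 149.6 | 117.0 | 32.6 |
| Restarted | 104.6 | 99.0 | 5.6 |

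Total over dropped is 32.6/10.2 = 3.2. Changing m scales every difference by the same factor, so the ratio does not depend on the 60 s.

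**Simulation of the tests.** 69 per arm, 8,000 replicates; lognormal attempt time (median 40 s, sigma 0.6) and lognormal search between sticks (median 60 s, sigma 0.6); other assumptions as above. Differences are standard minus device, in seconds. The last column is how often the dropped and total ANOVAs disagree at p<0.05.

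| Three-attempt success, standard vs device | Dropped | End of attempt 3 | Total | Restarted | Disagree |
|---|---|---|---|---|---|
| 75% vs 90% | 19.9 | 41.2 | 64.7 | 10.9 | 39.8% |
| 80% vs 90% | 15.0 | 29.5 | 45.2 | 9.5 | 27.0% |
| 85% vs 90% | 8.3 | 16.1 | 24.5 | 5.9 | 15.1% |
| 98.4% vs 99.9% | 21.4 | 24.4 | 26.3 | 21.1 | 11.5% |

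Total over dropped in the first row is 64.7/19.9 = 3.3. The seconds are about twice those of the closed form, but the ratio is nearly the same.

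The last row is the other reading of Section 8.2, with 90% and an assumed 75% as first-attempt rates: 1 − 0.1³ = 0.999 and 1 − 0.25³ = 0.984. Total over dropped is then 26.3/21.4 = 1.2.

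**Equal failure.** With 90% three-attempt success in both arms, and 80 s against 60 s per stick, the closed form gives 30.7, 33.6, 29.9 and 23.9 s for the four readings in order.

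**Sensitivity to rescue.** At 75% vs 90%, setting rescue per-stick success between 0.4 and 0.8 in both arms moves the total difference from 87 to 64 s and the restarted one from 33 to 10 s. The other two readings do not depend on it.

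**Power.** At 75% vs 90%: dropped 17%, end of attempt 3 54%, total 47%, restarted 9%, log-rank with failures kept as not achieved 73%. Chi-square on the primary endpoint has 66%. If the device only shortens times by 20%, with per-stick success 0.60 in both arms, log-rank has about 15% and ANOVA with failures dropped about 26%.

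**The case against.** **The size is conditional.** A reader might infer that the readings always give clearly different results. The documents do not support that: they give no times and no standard-arm rate. Section 2.2 puts first-attempt success as high as 92%, and Section 7.2.1 restricts insertion to experienced staff, so failure may be rare. Section 2.1 calls infants especially challenging, so common failure is possible but not established. Even when failure is common, some pairs stay close (8.3 against 5.9 s at 85% vs 90%). This objection stands and limits the claim.

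**The readings are not equally open.** Section 7.2.1 gives one starting point and then names the same measure again, which favours one continuous clock. The restarted clock is the weakest reading.

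**Type I error.** A reader might infer that it is inflated. Any one reading fixed in advance rejects in about 5% of null trials. Taking the best of the dropped, total and restarted readings gives about 10% at 90% success in both arms, but only if the choice follows the data, and it counts the weakest reading. The documents do not show such a choice.

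**A reversed conclusion.** All readings have the same sign in the cases tabled above. A reversal needed a specially constructed mix of easy and difficult children, and is not relied on.

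**The remedy.** One sentence fixing the value would close the gap, and total time by arm is a legitimate choice. Log-rank largely repeats the primary comparison: 74%, 43% and 17% power, against 66%, 37% and 15% for chi-square, at standard success of 75%, 80% and 85%. This cost is real. What remains is that ANOVA with failures dropped selects on the primary outcome, and no other value is defined.

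**Conclusion.** The gap is real and confined to the secondary time endpoint. Sections 7.2.1 and 8.3 together leave a three-stick failure without a time, so the ANOVA either selects on the primary outcome or uses an undefined value.

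The consequence is large only if three-stick failure is common and differs between arms. At an assumed 75% vs 90%, total time gives about three times the difference seen with failures dropped, and the two tests disagree in roughly 40% of trials. If failure is rare or equal between arms, the estimated differences are close and the choice matters little. That includes the case where the 90% in Section 8.2 means first-attempt success and the standard arm is not far behind.

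The ratio of about three held in both models; the seconds are model-dependent. The plan should be changed, but this does not threaten the trial's main result.

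**What to change.** In Section 8.3, replace ANOVA for times with one pre-specified comparison by randomised arm: time from first skin contact to success on the assigned technique, by Kaplan-Meier and log-rank test. Keep three-stick failures in the analysis as not achieved beyond the longest observed time.

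Report total time from first skin contact through rescue, by randomised arm, as a separate supplementary question. It is not a sensitivity analysis of the first, because it asks something different.

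In Section 7.2.1, state that the recorded rescue time also runs from first skin contact.

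Report by arm the children withdrawn after randomisation under Sections 3.3.1 and 7.2.1, and state whether they are censored at withdrawal or excluded from the time analysis.

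**Cost.** A few sentences in Section 8.3, one in 7.2.1, and no extra procedure. The data form must hold the clock times of first skin contact, of success, and of success under rescue. The software must offer Kaplan-Meier and log-rank.

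**Downside.** The log-rank result largely follows the primary endpoint and has less power than ANOVA if the device only speeds insertion (about 15% against 26%, illustrative).
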